### Recruitment Script

This is a general script, but can be changed as needed for each situation.

*“Hi, \_\_\_\_! My name is \_\_\_\_ and I am part of the research staff with the Department of Preventive Medicine at the University of Tennessee Health Science Center. You’re here today because you agreed to speak with us about your feelings about drug and alcohol use, and you’re open to hearing about treatment options. We’re doing a research study where we ask people questions, have a discussion, and then ask a few more questions.*

*If you think you might be interested in being in this study, I can ask you a few questions to see if you’re eligible, then we can go through a consent form with you to help you decide if you’d like to participate. Are you interested in seeing if you’re eligible?*

If a person does not wish to participate, we can still provide a handout or information about how to get treatment.

## Consent

The consent of the adult subject will be obtained at the first study visit at baseline after assessing for eligibility but before any identifying data collection begins.

Inviting the subject to read and sign the consent form is not sufficient for securing informed consent. Study staff will go through the consent form with the participant, reviewing all elements of informed consent as stated in 21 CFR 50 § B and will answer all questions regarding the study.

A copy of the informed consent will be given to the subject and the original(s) will be placed in the subjects' research record. An entry documenting informed consent must also be made in the subjects' research record to confirm that informed consent was obtained prior to any study-related procedures and that the subject received a signed copy. The objection of any subject in word or action to the performance of study procedures will be sufficient for their withdrawal or exclusion from the study. Study procedures will not continue until a signed consent form is received.

### **Electronic Consent**

This project received approval for alteration of consent through the UTHSC IRB. In circumstances where a participant is unable to consent in person due to COVID restrictions, the participant may be consented using DocuSign.

All standard procedures for consent must be followed including the participant being able to view the document while staff reviews with them, having sufficient time to review the document and ask questions, etc.

### **Intervention**

The Intrapersonal Stigma Reduction Intervention will address the stigma of addiction, education about addiction, life goals, deciding whether to disclose addiction, and links to services. These modules are covered in an effort to encourage the occurrence of the first treatment visit at the Center for Addiction Science. See Appendix A for the full intervention script.

### **Data Collection**

Whether in-person or on the phone, research staff will read aloud the items from each measure for the participant to answer. The staff member will record the responses on the paper forms and will later enter the data electronically.

### **Incentives**

#### **Gift Card Distribution**

Participants will receive \$20 upon completion of each visit (baseline and follow-up) in the form of a Kroger gift card. The gift cards will be photocopied or scanned onto the gift card receipt. The staff member will take the receipt, gift cards, and a computer back into the room with the participant and check the gift card balance on the Kroger website before distributing. Once the balance is verified, the staff member will fill out the receipt in front of the participant. Both the

research staff and the participant will sign the receipt verifying the information to be true. We will provide a copy of the receipt to the participant.

### **Gift Card Storage**

Since this project is remote and we will not have ready access to a safe, a minimal number of gift cards should be checked out each week and stored in the locked briefcase with other study documents. Gift cards should only be checked out of the safe when they are ready to be disbursed to a participant. The remaining gift cards will be kept in the safe on the 6th floor of the Pauline Building. The gift card log will be kept in the safe and filled out each time a gift card is moved in or out of the safe.

### **Adverse Events**

Adverse events (AE's) are defined as any unfavorable medical occurrence in a human subject, including any abnormal sign, symptom, or disease temporally associated with the subject's participation in the research, whether or not considered related to the subject's participation in the research.

Serious adverse events (SAE's) are any adverse event temporally associated with the subject's participation in research that meets any of the following criteria:

- Results in death
- Is life-threatening (places the subject at immediate risk of death from the event as it occurred)
- Requires inpatient hospitalization or prolongation of existing hospitalization;
- Results in a persistent or significant disability/incapacity;
- Results in a congenital anomaly
- Any other adverse event that, based upon appropriate medical judgment, may jeopardize the subject's health and may require medical or surgical intervention to prevent one of the other outcomes listed in this definition

If a participant experiences any adverse event during the course of the study, we will conduct an assessment, complete an Adverse Event form, and follow the adverse event reporting system as required by our IRB and NIH regulations.

All SAE's that are potentially related to the study are to be reported to the Project Coordinator ([name]) within one working day. The Project Coordinator will review and escalate to the PI via email within 48 hours of initial documentation.

UTHSC's IRB operating procedures regarding AE's can be found here:  
<https://www.uthsc.edu/research/compliance/irb/researchers/documents/adverse-event-reporting.pdf>

## Retention

It is the job of the research staff to retain all participants in the study in an attempt to have all participants complete their follow up visit. Staff will use various retention efforts to remain in contact with the participants after enrollment. Staff will also send participants an appointment reminder via text the day before their follow up visit (or via phone if preferred by participant).

Participants will have an additional 2 weeks to make up their missed appointment in order to provide us with the data and so they may receive their compensation. The following retention efforts should be made:

1. Calling the participant to check in and/or offer another date to reschedule.
2. Texting the participant to offer another date.
3. Emailing the participant.
4. Mailing a letter to the most recent address on file.

The research staff will cycle through these retention efforts during the 2 weeks to ensure they are doing their due diligence to contact the participant. The visit can be completed over-the-phone or in-person.

## MEASURES

### Assessment Schedule

Measure	Baseline	Follow-Up
Contact Information	X	
Demographics	X	
Substance Use Stigma Mechanisms Scale (SU-SMS)	X	X
Agreement to set up intake visit at Center for Addiction Science (or other treatment facility)	X	
Attendance at intake visit at Center for Addiction Science (or other treatment facility)		X

**CONTACT INFORMATION**

First:	
Middle:	
Last:	

Street:	
Apt/Suite:	
City/State/Zip:	

Email:	
--------	--

Primary Phone:		
Can we leave a voicemail?	Yes	No
Can we send a text?	Yes	No
Secondary Phone:		
Can we leave a voicemail?	Yes	No
Can we send a text?	Yes	No

DEMOGRAPHICS			
Date of Birth:			
Gender:	Male	Female	Transgender
Sex at birth:	Male	Female	
Race (circle all that apply):	African American or Black	White	Alaskan Native
	Pacific Islander	Native American	Other: _____
Are you of Spanish, Hispanic, or Latino origin?	Yes	No	

Current Marital Status:	Married or living as married	Widowed	Divorced
	Separated	Single, never married	

Current Household Income per year:	Less than \$10,000	\$10,000-19,999	\$20,000-29,999	\$30,000-39,999
	\$40,000-49,999	\$50,000-59,999	\$60,000-69,999	\$70,000-79,999
	\$80,000-89,999	\$90,000-99,999	Over \$100,000	Unsure

Highest level of schooling completed:	8 th grade or less	9 th -11 th grade	12 th grade or GED	Associate's degree
	Vocational or Trade School	Some college	Bachelor's degree	Graduate degree

## SU-SMS

How often have people treated you this way in the past because of your alcohol and/or drug use history?  
Please circle your response.

		Never	Not often	Somewhat often	Often	Very Often
1.	Family members have thought that I cannot be trusted.	1	2	3	4	5
2.	Family members have looked down on me.	1	2	3	4	5
3.	Family members have treated me differently.	1	2	3	4	5
4.	Healthcare workers have not listened to my concerns.	1	2	3	4	5
5.	Healthcare workers have thought that I'm pill shopping, or trying to con them into giving me prescription medications to get high or sell.	1	2	3	4	5
6.	Healthcare workers have given me poor care.	1	2	3	4	5

How likely is it that people will treat you in the following ways in the future because of your alcohol and/or drug use history?

		Very unlikely	Unlikely	Neither unlikely nor likely	Likely	Very likely

1.	Family members will think that I cannot be trusted.	1	2	3	4	5
2.	Family members will look down on me.	1	2	3	4	5
3.	Family members will treat me differently.	1	2	3	4	5
4.	Healthcare workers will not listen to my concerns.	1	2	3	4	5
5.	Healthcare workers will think that I'm pill shopping, or trying to con them into giving me prescription medications to get high or sell.	1	2	3	4	5
6.	Healthcare workers will give me poor care.	1	2	3	4	5

How do you feel about your alcohol and/or drug use history?

		Strongly disagree	Disagree	Neither disagree nor agree	Agree	Strongly agree
1.	Having used alcohol and/or drugs makes me feel like I'm a bad person.	1	2	3	4	5
2.	I feel I'm not as good as others because I used alcohol and/or drugs.	1	2	3	4	5
3.	I feel ashamed of having used alcohol and/or drugs.	1	2	3	4	5

4.	I think less of myself because I used alcohol and/or drugs.	1	2	3	4	5
5.	Having used alcohol and/or drugs makes me feel unclean.	1	2	3	4	5
6.	Having used alcohol and/or drugs is disgusting to me.	1	2	3	4	5

TREATMENT INITIATION		
Did you go to any facility for substance use treatment since we last spoke?	Yes	No
If yes, where did you get treatment?		

FEEDBACK & TREATMENT SATISFACTION				
1.	How interesting did you find this study?	Totally bad, boring	OK	Excellent, it was great
2.	What made you want to enroll in this study? (select all that apply)	I wanted help getting treatment	Gift cards	Other _____
3.	How personally relevant did you find this study?	Not at all relevant	Somewhat relevant	Very relevant
4.	How effective do you think this study was in helping you start treatment?	Not at all effective	Somewhat effective	Very Effective
5.	For those who haven't sought treatment: How likely you are to seek treatment in the near future?	Unlikely	Unsure	Likely
6.	How effective, overall, do you think this program will be in helping substance users seek treatment?	1 = Not useful or effective 10 = Highly effective. The best treatment I could imagine.		

7.	What was the most effective part of this study for you?	(Open ended)
8.	Can you think of any ways to make this study more effective and user-friendly?	(Open ended)

## OTHER DOCUMENTATION

## **Gift Card Log – Example**

## Kroger \$20 Gift Cards

## Gift Card Receipt

**Study ID** \_\_\_\_\_

The participant and I, the research staff member, checked the balance of the gift card before distribution.

We discussed that the Research Study is not responsible for and will not replace lost or stolen gift cards once the gift card has been disbursed.

Date	____ / ____ / ____		
Staff Initials	_____	GC Amount	\$ _____
Participant Initials	_____	Quantity	_____

Reducing Stigma towards Opioid Use Disorder on Interpersonal and Intrapersonal Levels

Statistical Analysis Plan

NCT04693416

12/7/2022

Preliminary data analyses will include studies of patterns of missing data, dropout rates, distributional properties of measures, and correlations among assessment measures. Continuous variables showing significant skewness or kurtosis will be analyzed with methods not sensitive to these features or will be transformed using standard approaches (such as Box-Cox transformations). Because all analyses will focus on feasibility and satisfaction and determining preliminary intervention effect sizes (with less concern focused on testing for statistical significance), outcome analyses will be conducted using a separate analysis for each outcome at the follow up observation.

Individual (intrapersonal) changes in stigma pre/post intervention will be conducted using paired sample t-test/Wilcoxon signed-rank test. Individual treatment uptake (agreement to set up an appointment and attendance at the appointment) will be included as secondary correlational analyses to evaluate relations with stigma scores. Comparisons with archival data will be conducted using a Chi Square analysis/Fisher's exact test. Family/Support (interpersonal) pre/post intervention outcomes will be conducted using paired sample t-test/Wilcoxon signed-rank test. Community assessment baseline and follow up data will be entered into a 2 (baseline vs. follow up) by 2 (intervention vs. comparison) analysis of variance (ANOVA) which will yield effect sizes for time, and interactions of time by intervention group. The primary dependent variable will be stigma score. We hypothesize that stigma scores will be lower in the intervention community.

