## PREFACE

The purpose of this document is to provide a Manual of Operating Procedures (MOP) for the SMART Supplement Project 5a — Intrapersonal Stigma Reduction. The role of the MOP is to facilitate consistency in protocol implementation and data collection across participants and study staff. Use of the MOP increases the likelihood that the results of the study will be scientifically credible and provides reassurance that participant safety and scientific integrity are closely monitored.

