## OVERVIEW

### Objectives

The goal of this project is to develop and evaluate the efficacy of a stigma reduction intervention that functions at the Intrapersonal (individual) level. Our intervention will address this cost/benefit evaluation among individuals known to face intersecting stigma of alcohol or substance use disorder and African American race, with treatment elements chosen explicitly to increase the value of treatment using salient forms of reward, and to ease perceived costs through explicit services in an effort to encourage the occurrence of the first treatment visit.

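### Does the SAP leave open which ANOVA effect answers its community hypothesis?

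*SAP*

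**What the plan says.** The SAP has no numbered sections. Its second paragraph puts the community baseline and follow-up data into an ANOVA with two factors, time and community group, "which will yield effect sizes for time, and interactions of time by intervention group". It adds that "The primary dependent variable will be stigma score" and closes with the hypothesis: "We hypothesize that stigma scores will be lower in the intervention community".

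Two statements in the first paragraph bear on how this is read. One is general and covers every outcome: "outcome analyses will be conducted using a separate analysis for each outcome at the follow up observation". The other sets the purpose as feasibility, satisfaction and preliminary effect sizes, "with less concern focused on testing for statistical significance".

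The protocol does not help. Its Preface identifies it as the manual for "SMART Supplement Project 5a — Intrapersonal Stigma Reduction", and its Objectives section says the aim is to "develop and evaluate the efficacy of a stigma reduction intervention that functions at the Intrapersonal (individual) level". It contains no community comparison.

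**The concern.** The hypothesis concerns where the scores stand, whereas the interaction concerns how far they move. The SAP does not say that the second answers the first. The first paragraph's reference to the follow-up observation could even be taken to supply the missing time point, which would suggest comparing the two communities at follow-up alone.

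That would matter if the communities differed at the start. The supplied documents describe no randomisation, matching or balance check for them, so equal baselines cannot be assumed. A hypothesis judged on level could then appear confirmed with no intervention effect, or appear to fail when stigma did fall. An emphasis on effect sizes over significance tests gives no protection, because the effect size itself would be shifted by the gap.

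**Working it through.** The documents state no figure for the community analysis, so there is none to reproduce. The check has two parts: what each possible contrast estimates, and which of them the SAP plans.

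**What each contrast estimates.** Let the comparison community have mean m at baseline and m + c at follow-up. Let the intervention community have m + g at baseline and m + g + c + d at follow-up. Here g is the baseline gap (intervention minus comparison), c the change common to both, and d the intervention effect.

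- Follow-up difference: (m + g + c + d) - (m + c) = g + d
- Group difference averaged over waves: [g + (g + d)]/2 = g + d/2
- Time effect averaged over communities: [(c + d) + c]/2 = c + d/2
- Time-by-group interaction: (c + d) - c = d

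Assumed cell means on a 1-to-5 scale, with c = 0, show the differences. These values are illustrative and do not come from the documents.

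| Case | Intervention, baseline / follow-up | Comparison, baseline / follow-up | Follow-up difference | Wave-averaged difference | Time effect | Interaction |
|---|---|---|---|---|---|---|
| A: g = -0.3, d = 0 | 2.7 / 2.7 | 3.0 / 3.0 | -0.30 | -0.30 | 0.00 | 0.00 |
| B: g = 0, d = -0.3 | 3.0 / 2.7 | 3.0 / 3.0 | -0.30 | -0.15 | -0.15 | -0.30 |
| C: g = +0.3, d = -0.3 | 3.3 / 3.0 | 3.0 / 3.0 | 0.00 | +0.15 | -0.15 | -0.30 |

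The choice of contrast therefore matters. Case A would appear to confirm a hypothesis about level with no effect present. Case C would hide a real fall of 0.30. The interaction returns d in all three cases.

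**Which contrasts the SAP plans.**

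1. *Wave-averaged group difference.* This is the group main effect. The SAP's list of ANOVA effects omits it.
2. *Follow-up difference.* No two-group comparison of community stigma at follow-up appears anywhere in the SAP. The sentence that seems to suggest one is the general statement in the first paragraph. The second paragraph then gives each stigma outcome an analysis that uses baseline: paired tests for the individual and family outcomes, and the time-by-community ANOVA for the community. The general sentence therefore cannot mean that baseline is ignored for stigma. It is better read as one analysis per outcome at the single follow-up occasion, and the specific text governs.
3. *Time effect.* This is listed, but it pools the two communities (c + d/2) and cannot say which is lower.
4. *Interaction.* This is listed, and it is the only listed effect that compares the communities.

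By elimination, the hypothesis can be answered from the planned output only through the interaction.

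**The case for a change.** The strongest case on the other side is that inferring an intention is weaker than specifying it. The literal wording describes a level, no sentence links it to the interaction, and a standard two-by-two ANOVA also prints a group main effect, which someone could report. The consequences would be real. If one assumes 50 respondents per community, a 0.3 SD baseline gap and no intervention effect, a follow-up-only test at the two-sided 5% level would be significant in about 32% of trials. Tying the hypothesis to the interaction would cost one sentence.

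The textual point stands: the hypothesis has no time point and is not matched to a model term. The algebra stands as well. The error rate does not count against this plan. It describes a test the SAP does not list, it uses a sample size and a gap that the documents do not give, and it measures significance in a plan that sets no significance level. With an error term that fits the sampling, the interaction holds its 5%.

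Two related matters are sometimes attached to this point: the error term if the same people are surveyed twice, and the limits of a comparison with one community per arm. They are separate questions about sampling and clustering. The hypothesis sentence neither causes nor settles them, and an analyst would address both when fitting and reporting the model. How the communities were chosen may also be set out in community-project documents outside this set, so their silence here shows only that the gap is unknown.

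**Conclusion.** No change is needed. The hypothesis is loosely worded, but the analysis beside it is specified well enough: the interaction is planned, it is the only listed effect that compares the communities, and a stable baseline gap does not bias it. Carrying out the SAP as written gives the difference in change between communities. Rewording the hypothesis as a larger fall in the intervention community would be harmless, but it would alter no data, model or reported effect size.

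This rests on two conditions. The first is that the analyst reports the effects the SAP lists and does not substitute an unlisted group main effect. The second is the usual assumption behind any difference in change, that both communities would otherwise have changed by the same amount (the common c above). The second would apply equally if the hypothesis were reworded. The possible distortion under a level reading equals the full baseline gap at follow-up, for example 0.30 for a gap of 0.3, but it arises only in contrasts the plan does not include.
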